11.0 SAFETY ANALYSES

All safety analyses will be based on the Safety Population.

11.1 Analysis of Dose-Limiting Toxicity

Dose finding for this study is based on the assessment of dose-limiting toxicity (DLT) of bempegaldesleukin dose levels. Number and percentage of patients with any DLT will be summarized by bempegaldesleukin dose level in bempegaldesleukin/SOC treatment groups and placebo for the Safety Population.

11.2 Adverse Events

An AE is defined as any untoward medical occurrence in a subject who is administered a medicinal product and that does not necessarily have a causal relationship to the treatment. All AEs will be included in the data listings. Verbatim terms on case report forms will be mapped to preferred terms and system organ classes (SOC) using the Medical Dictionary for Regulatory Activities (MedDRA) (version 20.0).

A Treatment-Emergent Adverse Event (TEAE) is defined as an adverse event that occurs on or after the treatment dose, and treatment-emergent period is from the study dose date to 30 days after the study dose. The TEAE summary will be displayed by treatment using treatment-emergent period. Unless otherwise specified, summaries that are displayed by SOC and preferred terms will be ordered alphabetically by SOC, and within each SOC, preferred terms will also be ordered alphabetically. Summaries of the following types will be presented:

- TEAEs by MedDRA SOC and preferred term.
- TEAEs by MedDRA SOC, preferred term, and worst CTCAE grade (version 5.0). At each level of subject summarization, a subject is classified according to the worst CTCAE grade if the subject reported one or more CTCAE grade.
- TEAEs related to study drug by MedDRA SOC, preferred term, and worst CTCAE grade.
- TEAEs by descending incidence of preferred terms.
- Serious TEAEs by MedDRA SOC, preferred term and worst CTCAE grade.
- Serious TEAEs related to study drug by MedDRA SOC, preferred term, and worst CTCAE grade.
- TEAEs leading to early termination by MedDRA SOC, preferred term, and worst CTCAE grade.
- Any Grade \geq 3 drug-related AE.
- Respiratory compromise or other virus-related AE attributed to worsening COVID-19, such as severe hypoxia, cyanosis, or chest pain/pressure.
- TEAEs leading to deaths.

For each subject and for each adverse event, the duration of the event (days) will be calculated as:

Duration of AE (Days) = AE stop date - AE start date +1.

The duration of AEs will be displayed in the data listing.

11.3 Medical History

An event occurring after the patient has provided informed consent, but before the first dose of study treatment, will be collected as medical history unless the event is either new and attributed to protocol-mandated procedures by the Investigator or there is a significant change in the rate of occurrence or an increase in the severity of the pre-existing condition which is judged to be clinically important and attributed to the protocol-mandated procedures by the Investigator. Under the latter 2 circumstances, the event will be considered an AE and will be captured as such.

Medical history will be listed and summarized by System Organ Class and Preferred Term.

11.4 Visit Window for Safety Endpoints:

If more than one value is obtained for the same measure within a given visit window, the value closest to the planned study visit day/time will be used for reporting and analysis. If multiple values are the same number of days/times away from the nominal visit day/time, the latter one will be used.

11.5 Clinical Laboratory Evaluation

Hematology and chemistry parameters will be summarized using descriptive statistics at baseline and post-dose. Changes from baseline will also be summarized.

Shift tables will be provided to assess changes in laboratory values from baseline to worst post-dose CTCAE grade. Only non-missing assessments at baseline and post-dose will be analyzed.

Any clinically significant lab abnormalities will be determined by the Principal Investigator and will be reported in the AE table summaries.

11.6 Vital Signs

Vital signs, including oxygen saturation (SpO₂), will be summarized using descriptive statistics at baseline and at each post-dose time point. Changes from baseline will also be summarized using descriptive statistics.

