4.0 SELECTION OF STUDY POPULATION

4.1 Inclusion Criteria

Each patient will be entered into this study only if he/she meets all the following criteria:

- 1. Patient (or legally authorized representative) provides written, informed consent to participate in the study and follow the study procedures. The Investigator takes responsibility for ensuring that all vulnerable patients are protected and participate voluntarily in an environment free from coercion or undue influence.
- 2. Male or female patients, age 18 years or older on the day of signing the informed consent form (ICF).
- 3. Agrees to admission to an in-patient facility for monitoring from Days 1 to 8, inclusive.
- 4. Symptoms of mild illness with COVID-19 (eg, fever, cough, sore throat, malaise, headache, muscle pain, gastrointestinal symptoms) without shortness of breath, dyspnea, or clinical signs indicative of more serious COVID-19.
- 5. Confirmed COVID-19 determined by a positive, documented SARS-CoV-2 infection determined by a commercial or public health assay in any specimen within 4 days prior to the screening visit or during the 7-day screening period.
- 6. Respiratory rate < 20 breaths per minute.
- 7. Heart rate < 90 bpm.
- 8. Oxygen saturation by pulse oximetry > 93% on room air.
- 9. Body mass index $< 35 \text{ kg/m}^2$.
- 10. Demonstrated adequate organ function, as defined below:
 - a. Absolute neutrophil count (ANC) $\geq 1500/\mu L$ ($\geq 1000/\mu L$ for patients with known or suspected diagnosis of benign ethnic neutropenia)
 - b. Platelet count $\geq 100 \times 10^3/\mu L$
 - c. Hemoglobin $\ge 12.0 \text{ g/dL}$
 - d. Estimated glomerular filtration rate (eGFR) \ge 30 mL/min, where eGFR is estimated by the Modification of Diet Renal Disease (MDRD) equation: eGFR (mL/min/1.73 m²) = 175 × (serum creatinine)^{-1.154} × (age)^{-0.203} × (0.742 if female) × (1.212 if black)
 - e. Alanine transaminase (ALT) or aspartate transaminase (AST) or < 2 × upper limit of normal (ULN)
 - f. Total bilirubin $< 1.5 \times$ ULN

- 11. Reproductive Status
 - a. Women of childbearing potential (WOCBP) must have a negative serum or urine pregnancy test (minimum sensitivity 25 IU/L or equivalent units of human chorionic gonadotropin [HCG]) within the 7 days prior to enrollment.
 - b. Women must not be breastfeeding.

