7.14 Vital Signs

Vital sign measurements will be recorded according to the Schedule of Events (Section 1.2). Vital signs include pulse rate, respiratory rate, systolic and diastolic blood pressure, oxygen saturation, and temperature. It is preferred that the same arm be used for all blood pressure readings, if possible. Weight is to be reported at screening and on the day of dosing, height at screening visit only.

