8.0 ASSESSMENT OF DISEASE MEASUREMENT

8.1 **Disease Measurement Assessments**

Screening and follow-up assessments should be acquired as outlined in Section 1.2.

8.1.1 **Measures of Clinical Support and Limitations**

The following measures of clinical support will be assessed at the first assessment of a given study day as outlined in Section 1.2:

- Limitations of physical activity.
- Hospitalization status (yes versus no).
- Oxygen requirement by mask or nasal prongs.
- Oxygen by non-invasive ventilation or high-flow.
- Intubation and mechanical ventilation requirement.
- ECMO requirement.

8.1.2 **WHO Clinical Progression Scale**

Table 13 provides the WHO Clinical Progression Scale, an 11-point clinical status ordinal scale, which will be used to measure COVID-19 clinical status and resource use over the course of the study (WHO 2020). The scale is an assessment of the clinical status at the first assessment of a given study day.

Table 13:	WHO Clinical Progression Scale
-----------	--------------------------------

Patient state	Descriptor	Score
Uninfected	Uninfected; no viral RNA detected	0
Ambulatory mild	Asymptomatic; viral RNA detected	1
disease	Symptomatic; independent	2
	Symptomatic; assistance needed	3
Hospitalized:	Hospitalized, no oxygen therapy ^a	4
Moderate disease	Hospitalized; oxygen by mask or nasal prongs	5
Hospitalized:	Hospitalized; oxygen by non-invasive ventilation or high-flow	6
Severe disease	Intubation and mechanical ventilation, $PaO_2/FiO_2 \ge 150$ or $SpO_2/FiO_2 \ge 200$	7
	Mechanical ventilation, $PaO_2/FiO_2 < 150$ (SpO ₂ /FiO ₂ < 200) or vasopressors	8
	Mechanical ventilation, $PaO_2/FiO_2 < 150$ and vasopressors, dialysis, or ECMO	9
Dead	Death	10

Abbreviations: ECMO = extracorporeal membrane oxygenation; FiO_2 = fraction of inspired oxygen; PaO_2 = partial pressure of arterial oxygen; $SpO_2 = oxygen$ saturation

a. If hospitalized for isolation only, record status as for ambulatory patient.

Source: WHO 2020

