5.0 GENERAL ANALYSIS CONSIDERATIONS

The statistical analyses will be reported using summary tables and data listings. Continuous variables will be summarized with means, standard deviations, medians, minimums, and maximums. Categorical variables will be summarized by counts and by percentage of patients in

corresponding categories. All summary tables will be presented by treatment. For patients who receive placebo, the data will be pooled as one placebo group.

Individual subject data obtained from the case report forms (CRFs) and any derived data will be presented by subject in data listings. Data listings will be sorted by the treatment group, subject, visit date, and time, if applicable.

All analyses and tabulations will be performed using SAS Version 9.4 or higher. All outputs will be presented in rich text format (RTF).

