5.1 Definition of Common Variables

- Reference date (Day 1) = first dose date of study medication. If a patient has not been treated, the reference day will be set as missing.
- Study Day = assessment date reference date + 1 for assessments performed on or after the reference date or assessment date reference date for assessments performed before the reference date.
- Baseline: Baseline will be defined as the last non-missing value on or before the date of administration of the first dose of study medication (and time if available) unless it is identifiable by time that the value is after the first dose. For patients who have been not treated with any dose, then the baseline is defined as the screening value.

Time on study will be calculated as follows:

For visits/assessments/medications/therapies on or post study drug:

- Study hour will be calculated as follows:
- Study Hour = (assessment date time date time of the start of the first study dose)/60
- Study Day = (assessment date date of the first study dose) + 1, if assessment date is on or after the study dose date in that cohort
- Study Day = (assessment date date of the first study dose), if assessment date is prior to the study dose date in that cohort

For visit window derivation purpose, Study Day will be derived as ceiling of (Study Hour)/24.

For purposes of analysis and data display (i.e., means over time), actual visit hours/days are mapped to the planned study visit (i.e., nominal visits such as Hour 1, 2, Day 2, etc.) using visit windows. Acceptable visit windows around each scheduled procedure visit will be given for each measurement in the forthcoming sections. Due to the different data collection schedules for the various measurements, however, visit windows for different parameters might not be identical.

Unless otherwise specified, in mean and mean change from baseline/pre-dose summaries or analyses, if more than one value is obtained for the same measure within a given visit window,

the value closest to the planned study visit day and/or time will be used for reporting and analysis. If multiple values are equally away from the nominal visit day and/or time, the latter one will be used. However, for shift tables, the worst value mapped to that visit window will be used for summary purposes.

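### SAP 11.6 mixes room-air and on-oxygen SpO2 readings, so the SpO2 summary can understate desaturation and obscure a difference between arms

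*SAP*

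**What the plan says.** **The analysis.** SAP 11.6 states that vital signs, SpO2 among them, "will be summarized using descriptive statistics at baseline and at each post-dose time point". It adds: "Changes from baseline will also be summarized using descriptive statistics". SAP 5.0 fixes the statistics: "Continuous variables will be summarized with means, standard deviations, medians, minimums, and maximums". None of these sections has a rule for readings taken on supplemental oxygen.

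**The measurement.** Protocol 7.14 gives SpO2 by name only: "Vital signs include pulse rate, respiratory rate, systolic and diastolic blood pressure, oxygen saturation, and temperature". The Schedule of Events asks for it at screening, before dosing on Day 1, and every day until discharge, with no measurement condition. For SpO2, room air appears only as an entry requirement (Protocol 4.1): "Oxygen saturation by pulse oximetry > 93% on room air".

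**The value chosen.** SAP 5.1: "Baseline will be defined as the last non-missing value on or before the date of administration of the first dose of study medication". When several readings fall in one window, SAP 11.4 says "the value closest to the planned study visit day/time will be used for reporting and analysis". SAP 5.1 keeps the worst value for shift tables. SAP 11.5 plans a shift table for laboratory values; SAP 11.6 plans none for vital signs.

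**Oxygen use.** It is collected daily. Protocol 8.1.1 lists "Oxygen requirement by mask or nasal prongs", together with non-invasive or high-flow oxygen, ventilation and ECMO, all recorded at the first assessment of the study day.

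**The concern.** A change from baseline is interpretable when both readings are taken under the same condition. Here the baseline reading is untreated and the post-dose reading may be treated. Oxygen raises saturation, so whenever the selected reading is taken on oxygen the error runs toward no change, and it is larger in whichever arm uses more oxygen. Because the reading nearest the planned time is selected, and not the lowest, a nadir need not enter the table at all.

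Respiratory compromise, including severe hypoxia, is one of the DLT categories in Protocol 5.3.2.1.1, and vital signs are a named part of the safety evaluation. With 5 patients per active dose, one patient can decide how the table reads. A reader could find a flat SpO2 summary beside an oxygen-use table that is not flat, and have no means of reconciling the two.

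**Working it through.** **1. Is baseline on room air?** No passage says so for the predose reading, but three provisions make it so in effect. Protocol 4.1 requires room-air saturation above 93%. Protocol 4.2 excludes hypoxia and shortness of breath. Protocol 5.8 lists worsening beyond mild disease between screening and Day 1 as a reason to leave the study.

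**2. Is there a plan figure to reproduce?** No. SAP 4.0 makes no sample size calculation, and neither document gives an SpO2 mean, SD, expected fall or response to oxygen. Only the group sizes can be checked: 3 × (5 + 5) = 30, the planned total, and pooled placebo is 3 × 5 = 15.

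**3. Size, under assumptions.** One patient in a group of n falls by D points on room air, the selected reading has regained a share r of that fall, and everyone else changes by 0.

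- Mean change on room air: -D/n
- Mean change recorded: -D(1 - r)/n
- Hidden part: rD/n

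D and r are assumed. For n = 5:

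| D | Room air, -D/5 | Recorded, r = 0 | r = 0.5 | r = 0.75 | r = 1 |
|---|---|---|---|---|---|
| 5 | -1.0 | -1.0 | -0.5 | -0.25 | 0 |
| 8 | -1.6 | -1.6 | -0.8 | -0.4 | 0 |
| 12 | -2.4 | -2.4 | -1.2 | -0.6 | 0 |

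Here r = 0 is a reading taken before oxygen was started, and r = 1 is full correction. For n = 15, the room-air mean changes are -5/15 = -0.33, -8/15 = -0.53 and -12/15 = -0.80, again recorded as 0 when r = 1.

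**4. Between arms.** If that patient is in an active dose group and no placebo patient changes, the difference in mean change is -1.0 to -2.4 on room air. It is recorded as anything from that down to 0.

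**5. Does the reported minimum rescue the table?** Only in part. It is the minimum of the selected readings, so the patient's change enters as -D(1 - r): for r = 0.5, that is -2.5, -4 or -6 instead of -5, -8 or -12.

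**6. Would a room-air-only mean suffice?** No. It drops the patient who worsened. In the same example the other four changed by 0, so the room-air mean change is 0/4 = 0.

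**The case against.** The strongest reply is that the patient is counted elsewhere. SAP 7.6.1 tabulates oxygen need by treatment group. SAP 7.6.2 to 7.6.4 give WHO-scale shifts, status on Days 3, 5 and 8, and oxygen days (scores 5 to 9). Under Protocol 7.1, a vital-sign abnormality judged clinically significant, for example because it needs treatment, is an adverse event. It can then reach the respiratory summary in SAP 11.2 and, if adjudicated, the DLT table in SAP 11.1. SAP 5.0 also provides listings by subject, which are readable at 5 per group. No escalation or RP2D rule uses mean SpO2.

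All of that stands, and it limits the point. A reader might infer that the plan would miss respiratory harm; the documents do not support that. Nor do they make respiratory worsening the leading safety worry: Protocol 2.2.4.1 gives hypotension that place, and Protocol 7.9 names cytokine release syndrome as the event of special interest.

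The reply does not repair SAP 11.6. The other tables show that oxygen was given, not how far saturation fell, and nothing in them corrects the SpO2 change.

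**Conclusion.** The point holds for the SpO2 summary and no further. As written, SAP 11.6 can show little or no fall for a patient who desaturated and was given oxygen, and so can obscure a difference between arms. For one such patient among 5, with an assumed fall of 5 to 12 points, between 0 and 1.0 points (D = 5) or between 0 and 2.4 points (D = 12) of the group mean is hidden. The direction follows from the documents whenever the selected reading is on oxygen; the size does not.

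Two stronger readings are tempting. One is that such a patient always shows no fall. That is only the r = 1 end of the range: a reading before oxygen, or an incomplete correction, still shows a fall. The other is that the active arm would look better than placebo. With the remaining patients unchanged, that would need oxygen to lift readings above the patient's own baseline, and the documents give nothing on this.

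This is a worthwhile, inexpensive improvement to one safety summary. It does not affect sample size, error rates or the dose-finding rules.

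**What to change.** In SAP 11.6:

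- Flag each SpO2 value by that day's oxygen status, from the Protocol 8.1.1 items or a WHO score of 5 to 9. State the matching rule, because that status is taken at the first assessment of the day and oxygen may start or stop later.
- Add a categorical table by treatment group, for each day and for the worst post-dose day: room air above 93%, room air 93% or below, and on supplemental oxygen, ranked worst. The cut-point is borrowed from the entry criterion for analysis only.
- Report each patient's lowest post-dose SpO2, by treatment group.
- If room-air means are shown, put the number on oxygen beside them and do not interpret them alone, since they leave out the patients who worsened.
- Cross-refer to SAP 7.6.1 and 7.6.4.

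The cost is SAP wording and one extra table, built from data already collected daily. The limitation is that oxygen status is matched by day and not by reading, so some values will be misclassified on days when oxygen starts or stops. Recording oxygen status with each reading would remove that, but would change data collection.

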11.7 Electrocardiogram

ECG parameters (numeric) at baseline will be summarized using descriptive statistics.

The number and percentage of patients with abnormal (not clinically significant or clinically significant) and number and percentage of patients in each of the following categories based on QTcF at baseline will be provided in the safety Population:

- QTc interval \leq 450 ms,
- QTc interval > 480 ms,
- QTc interval > 500 ms.

12.0 CHANGES TO PROTOCOL-SPECIFIED ANALYSES

No changes from the protocol-specified analyses are planned.

